**6.3.1.3.2. Analysis of Pharmacokinetic Parameters**

If a PK parameter cannot be derived from a subject’s concentration data, the parameter will be coded as NC (ie, not calculated). (Note that NC values will not be generated beyond the day that a subject discontinues.)

In summary tables, statistics will be calculated by setting NC values to missing; and statistics will not be presented for a particular treatment if more than 50% of the data are NC.

If an individual subject has a known biased estimate of a PK parameter (due for example to an unexpected event such as incomplete administration of the IV infusion dose), this will be footnoted in summary tables and will not be included in the calculation of summary statistics.

*The PK parameters will be listed and summarized for subjects in the PK parameter analysis set. Parameters will be summarized by sequence, visit, and dose.*

*Each PK parameter will include the set of summary statistics as specified in the table below:*

Parameter	Summary Statistics
Cmax, AUCτ, Cav, Ctrough, CL, Vss, C2	N, arithmetic mean, median, cv%, standard deviation, minimum, maximum, geometric mean, geometric CV%
t1/2	N, arithmetic mean, median, cv%, standard deviation, minimum, maximum
Tmax	N, median, minimum, maximum

The following PK parameter summaries will be presented:

- All subjects (including those with additional PK sampling): Ctrough, C2, and for subjects in Sequence 2, also t1/2.
- Subjects with additional PK sampling: Ctrough, C2, Cmax, Tmax, AUCτ, Cav, CL, and for subjects in Sequence 2, also t1/2 and Vss.

Note Ctrough, C2, and t1/2 will be included in both summaries for the respective subject groups. Supporting data from the estimation of t1/2 will be listed for subjects in Sequence 2: the terminal phase rate constant (kel), goodness of fit statistic from the log-linear regression (r), and the first, last, and number of time points used in the estimation of kel.

Ctrough and C2 for the last dose of each dose escalation level will be summarized for Process 1 and Process 2 material as shown in the following table. For Process 1 material, these PK parameters will be obtained in Period 1. For Process 2 material, these PK parameters will be obtained from patients who received placebo in Period 1 and receive Process 2 material for the first time in Period 2.

090177e1909dd632\Approved\Approved On: 25-Mar-2019 05:54 (GMT)

Dose	Process 1 Data: Sequences 1 and 2 Period 1	Process 2 Data: Sequence 3 Period 2
5 mg	Week 13	Week 61
20 mg	Week 29	Week 77
40 mg	Week 45	Week 93

Only subjects with at least 4 consecutive doses of Process 2 material will be included in the Process 2 summaries.

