PD sample (Total GDF-8) q			X	X	X	X		X	X	X	X	X	X	X		
Biomarker Sample Group 1 (Prep D1.5)	X															
Biomarker Sample Group 2 (Prep B1.5, B2.5) j	X	X			X											
Biomarker Sample Group 3 (Prep R1, Cell-free RNA)	X															
Biomarker Sample Liver	X	X			X	X	X	X	X	X	X	X	X	X	X	X
Immunogenicity		X			X		X	X	X	X	X	X	X	X		
Wellness																
Wellness Phone Check r			X	X	X	X	X	X	X	X	X	X	X	X	X	X
Infusion Site Reaction monitoring			X	X	X	X	X	X	X	X	X	X	X	X	X	X
Adverse event monitoring			X	→	→	→	→	→	→	→	→	→	→	→	→	→
Concomitant medication			X	→	→	→	→	→	→	→	→	→	→	→	→	→

Abbreviations: → = ongoing/continuous monitoring; 6MWT=Six minute walk test; C-SSRS=Columbia Suicide Severity Rating Scale, DXA=Dual-energy x-ray absorptiometry; ECG = electrocardiogram; FSH= Follicle stimulating hormone; FVC=Forced vital capacity; GDF-8=growth differentiation factor 8; LH= Luteinizing hormone; MRI=magnetic resonance image; PD=Pharmacodynamics, PK=Pharmacokinetics, PODCI=Pediatric Outcomes Data Collection Instrument; PUL=Performance of Upper Limb, T4 =thyroxine; TIBC=Total iron binding capacity, TSH=thyroid stimulating hormone.

- a. The first 12 subjects will be required to complete 6 additional visits including Visit 4, 8, 10, 14, 16 and 20 (Day 8, 92, 120, 204, 232 and 316) to provide clinical laboratory and PK samples in Period 1. Subjects enrolled after the first 12 subjects will not be required to complete these additional visits.
- b. Assessments should be conducted on the Study Day within the visit window. In order to assure consistency in assessment collection, at visits where functional assessments and imaging assessments are collected at the same visit, subjects will be required to be assessed over a 2 day period. Please see [Section 6](#) for additional details.

- c. Informed consent must be provided by the subject's caregiver (parent or legal guardian). Subject will be required to provide assent in compliance local regulations and IRB requirements.
- d. Medical history will include confirmation by genetic testing of the diagnosis of Duchenne muscular dystrophy (DMD) as obtained from an approved laboratory. Results must confirm the presence of a mutation in the dystrophin gene(s) which is clinically consistent with the diagnosis of DMD.
- e. The physical examination will also include a nose and throat mucosal exam.
- f. Height and hormone testing should be performed in the morning.

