## **3. STUDY DESIGN**

### **3.1. Study Overview**

This is a Phase 2 randomized, 2-period, double-blind, placebo-controlled, multiple ascending dose study to evaluate the safety, efficacy, PK and PD of PF-06252616 administered to ambulatory boys diagnosed with DMD. Three IV infused dose levels will be investigated in a within subject dose escalating fashion.

PF-06252616 dose levels:

- 5 mg/kg
- 20 mg/kg
- 40 mg/kg

Depending on safety and PK data availability, alternative dose levels will be available and may be evaluated instead of or in addition to the planned dose levels. In Period 2, dosing may be adjusted based on the emerging safety and/or efficacy data.

Approximately 105 eligible subjects will be randomly assigned to 1 of 3 sequence groups and receive investigational product for approximately 96 weeks (2 treatment periods of approximately 48 weeks each) stratified by their baseline time to complete the 4 SC (either  $\leq$  or  $>8$  seconds).

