**Sequence 3 (n=35):**

Period 1: Placebo

Period 2: Active treatment (PF-06252616) within subject dose escalation (5, 20 and 40 mg/kg)

Each dose level will be explored in a dose escalating fashion within subjects, starting with the lowest dose. At each dose level, dosing will be administered over a 2-hour IV infusion every 4 weeks for a total of 16 weeks (4 doses). Dose escalation within a subject will occur following review of all available safety data through the planned fourth dose within each dose level. For example, in Period 1, there are three times when individual safety data will be reviewed for a determination of dose adjustment, at Week 13, Week 29 and Week 45 (every 4 months). In Period 2, there are two times when individual safety data are reviewed for a determination of dose adjustment, at Weeks 61 and 77 (every 4 months). Subjects will move from Period 1 to Period 2 without a pause between periods.

[figure not shown]
Subjects who complete this study through Week 97 may be invited to participate in an open-label-extension (OLE) study. Subjects, who have had a positive test result for ADA at any point during the study, *may* be asked to complete additional immunogenicity testing if warranted by other clinical safety findings prior to joining an extension study.

During the study, additional visits will be required to fully characterize PK and safety when subjects would not otherwise be returning for study drug administration. In order to limit the burden of the additional PK/safety assessments, only the first 12 subjects enrolled in the study will be asked to complete these additional PK visits. At each dose level, the first 12 subjects will be asked to return for testing 1 week after the first dose within each level and once again at 1 week after the last dose at each dose level. The additional PK/safety assessments will occur 6 times in Period 1. No additional visits would be required for these subjects in Period 2.

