**6.4. Visit 4, 8, 10, 14, 16, 20 (Day 8, 92, 120, 204, 232, 316) Additional PK visits**

The first 12 subjects enrolled in the study will be required to complete 6 additional visits to further characterize the PK profile of the study drug. Subjects enrolled after the first 12 subjects will not be required to complete these additional visits.

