#### **9.1. Sample Size Determination**

The sample size is based on the primary endpoint of demonstrating efficacy of change from baseline on a 4 stair climb timed function test as compared to placebo at 49 weeks. To detect a 2.5 second difference in change from baseline in 4 stair climb based on a difference between the active treatment and the placebo treatment in Period 1 assuming a common

standard deviation of 4.0 with 80% power at  $\alpha=0.05$  (two-sided), a 2:1 treatment allocation and one interim analysis a total of 96 subjects should complete 49 weeks of dosing for this assessment. Assuming a 10% attrition rate, approximately 105 subjects should be enrolled (70 subjects receiving PF-06252616 and 35 subjects receiving placebo) in order to ensure sufficient number of subjects will complete this assessment. If there are no safety issues and enrollment has completed, additional subjects may be enrolled prior to the time of the interim analysis. These additional subjects may help off-set any unforeseen variability that may occur outside the presumed standard deviation for this age group.

One interim analysis is planned to evaluate futility and efficacy after approximately 50% of the subjects have completed through Week 49. Alpha- and beta-spending functions will be used to determine the cutoffs for efficacy and futility at the interim based on the observed number of subjects in the interim analysis. The gamma family spending functions will be used to appropriately account for error spending and adjust for the observed information at the time of the interim analysis and conservative boundaries ( $\gamma \leq -1$ ) will be used to define the futility and efficacy boundaries. The cutoff used at the interim analysis will be calculated based on the percentage of subjects included at the interim analysis to ensure appropriate protection of the type I error. Further details regarding the interim analysis and simulations are included in the SAP.

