## 5. GENERAL METHODOLOGY AND CONVENTIONS

### 5.1. Hypotheses and Decision Rules

The assumed null and alternative hypotheses for testing the active treatment versus the placebo on the 4 stair climb are included below:

$$H_0: (\mu_{\text{active, 49 weeks}} - \mu_{\text{active, baseline}}) - (\mu_{\text{placebo, 49 weeks}} - \mu_{\text{placebo, baseline}}) = 0$$

$$H_1: (\mu_{\text{active, 49 weeks}} - \mu_{\text{active, baseline}}) - (\mu_{\text{placebo, 49 weeks}} - \mu_{\text{placebo, baseline}}) > 0$$

The primary efficacy analysis will be tested at  $\alpha=0.025$  (one-sided). The same type 1 error rate will be used for testing the secondary analyses. This test will be performed based on the data in period 1 from all subjects. Subjects assigned to sequence 1 and sequence 2 will be analyzed together in an active treatment group compared to subjects in sequence 3 (placebo during period 1).

The decision criteria for the interim analysis is described in CCI

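### The SAP summarises Cmax, Tmax, AUCtau, Cav and CL by sequence in Period 1, giving an expected 4 boys per cell, where combining Sequences 1 and 2 on their shared regimen would give about 8

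*SAP*

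**What the plan says.** SAP Section 6.3.1.3.2 sets the grouping for all PK parameter summaries: "Parameters will be summarized by sequence, visit, and dose". It names no combined summary of Sequences 1 and 2 for Cmax, Tmax, AUCtau, Cav or CL.

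SAP Table 1 and Section 6.3.1.3.1 limit these five parameters to boys with additional PK sampling, in Period 1: Cmax, Tmax, AUCtau and Cav at Weeks 1, 13, 17, 29, 33 and 45, and CL at Weeks 13, 29 and 45. Protocol Section 6.4 identifies those boys: "The first 12 subjects enrolled in the study will be required to complete 6 additional visits". Protocol Section 3.1 says the same ("only the first 12 subjects enrolled in the study will be asked to complete these additional PK visits"), as does the first footnote to the Period 1 schedule. No text restricts the 12 to the active sequences.

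Elsewhere the SAP does combine the two active sequences in Period 1. For efficacy, Section 5.1 says: "Subjects assigned to sequence 1 and sequence 2 will be analyzed together in an active treatment group compared to subjects in sequence 3". For the manufacturing-process comparison of C_trough and C2, the table in Section 6.3.1.3.2 has a column headed "Process 1 Data: Sequences 1 and 2 Period 1".

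**The concern.** Protocol Table 3 gives Sequences 1 and 2 the same dosing through Week 45: 5, then 20, then 40 mg/kg. They diverge at the Week 49 dose. The interval after the Week 45 dose closes with the Week 49 predose sample, so AUCtau, Cav and CL at Week 45 also precede the divergence. Boys who do not escalate as planned are already separated by the dose grouping. In Period 1, then, sequence labels two randomised halves of one planned regimen and carries no planned PK contrast.

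The split therefore falls on the parameters with the fewest boys, while parameters available in all boys are pooled in at least one table. What is at stake is how precisely the study report describes paediatric exposure and clearance for the secondary PK objective (S4 in SAP Section 2.1.2). A combined median cannot be recovered from two by-sequence tables, and Tmax is summarised only by N, median, minimum and maximum.

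**Working it through.** **Inputs**

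- Allocation: "Approximately 105 eligible subjects will be randomly assigned to 1 of 3 sequence groups" (Protocol 3.1), with 35 planned per sequence.
- Period 1 split: "70 subjects receiving PF-06252616 and 35 subjects receiving placebo" (Protocol 9.1).
- Boys with additional sampling: 12.
- Between-boy CV: not in the documents. I assume 30% and show 20% and 40%.

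**Reproducing the planned allocation.** 105 / 3 = 35 per sequence, and 2 × 35 = 70 on active drug in Period 1, against 35 on placebo. This matches the protocol. The documents state no cell size for the PK parameter tables.

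**Expected cell size**

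- One sequence: 12 × 1/3 = 4 boys.
- Sequences 1 and 2 combined: 12 × 2/3 = 8 boys.
- If the protocol's 10% attrition applied to these boys by Week 49: 4 × 0.9 = 3.6 and 8 × 0.9 = 7.2.

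These are expectations. The documents give no block size. Drawing 12 from 105 without blocking, the 95% range is 1 to 7 boys for one sequence and 5 to 11 for the two combined. A given sequence has 2 or fewer of the 12 with probability 16.5%. Under simple 1:1:1 allocation, Sequence 1 or Sequence 2 has 2 or fewer with probability about 35%. Blocking would lower both probabilities.

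**Precision.** On the log scale, s = sqrt(ln(1 + CV²)), and the 95% half-width is t(0.975, n−1) × s / sqrt(n).

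- n = 4: t / sqrt(n) = 3.182 / 2 = 1.591, so the half-width is 1.591 s.
- n = 8: t / sqrt(n) = 2.365 / 2.828 = 0.836, so the half-width is 0.836 s.
- Ratio: 1.591 / 0.836 = 1.90.

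The interval for a geometric mean, as a multiple of the estimate, is exp(± half-width):

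| Assumed CV | s | n = 4 | n = 8 |
|---|---|---|---|
| 20% | 0.198 | 0.73 to 1.37 | 0.85 to 1.18 |
| 30% | 0.294 | 0.63 to 1.60 | 0.78 to 1.28 |
| 40% | 0.385 | 0.54 to 1.85 | 0.72 to 1.38 |

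For 30% and n = 4: 1.591 × 0.294 = 0.467, and exp(±0.467) gives 0.63 and 1.60. The intervals measure how much information each cell holds; the SAP does not plan to report them.

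**The case against.** The strongest reply is that this is table layout. Section 6.3.1.3.2 plans only descriptive statistics for PK parameters, with no interval, test or decision rule, and individual values are listed, so any reader of the report can combine them. That stands, and it sets the size of the point.

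Four stronger readings are tempting, and the documents do not support them.

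- **That the split weakens the check of exposure against prediction.** Protocol Section 3.1 gives that check to unblinded clinical pharmacology scientists reviewing the first 12 boys, and does not describe it by sequence. The E-DMC receives PK data separately (Protocol 3.5.2), and any population PK analysis is reported separately (Protocol 9.2.4). None is tied to this table.
- **That four boys tell us almost nothing.** The smallest margin in Protocol Table 1 is 2.2 (Cmax at 40 mg/kg), while the widest upper limit above is 1.85 times the estimate. If exposure were near prediction, even that cell would lie below the limit as Table 1 assigns it. (Protocol 3.5.2 attaches the same two limit values to the opposite parameters, a separate matter to reconcile.)
- **That small cells would trip the rule withholding statistics when more than 50% of values are not calculated.** The rule is written per treatment, and Sequences 1 and 2 share a treatment in Period 1. Cmax and Tmax are read directly from the data and would seldom be missing for this reason.
- **That all concentration and GDF-8 summaries need the same change.** The all-subject PK concentration summary and the GDF-8 summaries rest on about 35 boys per sequence, so the small-cell reason does not apply. It applies only to the second concentration summary in SAP 6.3.1.4, limited to boys with additional sampling.

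It is also fair to say that the by-sequence tables have uses. Sequence 2's Week 45 CL belongs beside its Vss, which is computed from CL, and Sequence 1's Period 1 trough and end-of-infusion values are the natural reference for its own Period 2 values. A combined summary should therefore be added, not substituted.

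**Conclusion.** The point holds as a free improvement; it does not identify an error. For these five parameters the planned grouping gives an expected 4 boys per cell where about 8 are available on the same planned regimen, and the log-scale interval at 4 is 1.90 times as wide as at 8. The 4 and 8 assume that the 1:1:1 ratio carries through to the first 12 boys, which the documents do not guarantee. The interval figures rest on an assumed CV, though the 1.90 ratio does not. C_trough and C2 are less affected, being summarised in all boys and already combined in the process table; t1/2 and Vss are defined for Sequence 2 only and gain nothing from pooling.

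**What to change.** In SAP Section 6.3.1.3.2, add a sentence such as: For Period 1, Cmax, Tmax, AUCtau, Cav and CL will also be summarised by visit and dose with Sequences 1 and 2 combined. In Section 6.3.1.4, add the same combined Period 1 column to the concentration summary for subjects with additional PK sampling. Keep all by-sequence summaries, including Period 2 and Sequence 2's t1/2 and Vss. Leave the all-subject concentration and GDF-8 summaries as they are.

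The cost is SAP wording and a column in the table shells. No further data are needed. Protocol Section 9.2.4 does not prescribe grouping by sequence, so the addition does not conflict with it, and nothing now planned is lost.

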**2.3. Process 1 and Process 2 Material**

With the progression of the clinical development activities for PF-06252616, the current manufacturing process of PF-06252616 (referred to as Process 1) has been modified to a commercial-ready process (referred to as Process 2). Process 2 has improved productivity to meet commercial needs, but without change to the substance formulation. Changes from Process 1 and Process 2 include:

- Transition from the PF-06252616 100 mg/vial to a 260 mg/vial;
- Utilization of ½ the volume for reconstitution, while keeping post-reconstitution formulation identical.

The plan for introduction of Process 2 in this study is as follows and is dependent on individual subject status once Process 2 material becomes available:

- Any subject who receive Process 1 material will remain on Process 1 material throughout Period 1, but may be switched to Process 2 during Period 2. However, once Process 1 are depleted, Process 2 will be dispensed in Period 1 as well.
- Once a subject receives Process 2 material, he will only receive Process 2 material throughout remainder of participation.

Pharmacokinetic, pharmacodynamics and immunogenicity analyses will be performed in this study so as to confirm comparability of Process 1 and Process 2 materials, as further described in Section 6.3.1.3.2, 6.3.2.2, and 6.6.7, respectively.

090177e1909dd632\Approved\Approved On: 25-Mar-2019 05:54 (GMT)

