#### **6.6.7. Immunogenicity**

Immunogenicity analysis will be based on the immunogenicity analysis population which will be the same as the safety analysis population and will include anti-drug antibody and neutralizing antibody development by Week 97 and until the end of follow-up. Both continuous endpoints (titer) and categorical endpoints (ie, positive, negative and inconclusive) will be reported for the anti-drug antibody and neutralizing antibody assays by dose and sampling time points. Data permitting, the incidence of anti-drug antibody and

neutralizing antibody will be summarized by time points within each dose cohort, sequence, and may be also summarized by dose. The impact of anti-drug antibody and neutralizing antibody on PK and PD parameters and profiles, efficacy and safety may be also evaluated but no statistical inference will be drawn.

The immunogenicity of Process 1 material may be assessed from Sequence 1 and 2 for Period 1, and Sequence 2 of Period 2. To assess the immunogenicity of PF-06252616 Process 2 material, it is necessary that the subjects did not receive any prior administration of PF-06252616 Process 1 material. This may be obtained from subjects in Sequence 3 who received Placebo in Period 1 and receive drug product for the first time as Process 2 material in Period 2.

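### The Process 1 column of the Process 1/Process 2 comparison is defined by sequence and period, not by material received, so Process 2 data from Period 1 could enter it and dilute a difference

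*SAP*

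**What the plan says.** SAP Section 2.3 introduces Process 2, the commercial-ready manufacturing process, and gives the purpose of the comparison: "Pharmacokinetic, pharmacodynamics and immunogenicity analyses will be performed in this study so as to confirm comparability of Process 1 and Process 2 materials". On supply, a subject who has received Process 1 "will remain on Process 1 material throughout Period 1, but may be switched to Process 2 during Period 2". The next sentence makes an exception: "However, once Process 1 are depleted, Process 2 will be dispensed in Period 1 as well".

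SAP Section 6.3.1.3.2 sets out the PK comparison of C_trough and C2 at the last dose of each dose level. The text reads "For Process 1 material, these PK parameters will be obtained in Period 1", and the table column is headed "Process 1 Data: Sequences 1 and 2 Period 1", with Weeks 13, 29 and 45. The Process 2 column comes from Sequence 3 in Period 2 (Weeks 61, 77 and 93), that is, from subjects on placebo in Period 1 who meet active drug for the first time as Process 2. One filter on material follows: "Only subjects with at least 4 consecutive doses of Process 2 material will be included in the Process 2 summaries".

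SAP Section 6.3.2.2 has the GDF-8 trough summarised by process in the way already described for PK. SAP Section 6.6.7 says "The immunogenicity of Process 1 material may be assessed from Sequence 1 and 2 for Period 1" and adds Sequence 2 in Period 2. For Process 2 immunogenicity it requires that the subject had no earlier Process 1 dose.

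**The concern.** Section 2.3 foresees Process 2 vials reaching subjects on active drug in Period 1. Section 6.3.1.3.2 then labels Period 1 data from Sequences 1 and 2 as Process 1, without checking the vials used. A programmer working from the table would select by sequence, period and week. A Sequence 1 or 2 subject given Process 2 in Period 1 would then be counted as Process 1. He could not be counted as Process 2, because that column is confined to Sequence 3 in Period 2.

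The direction of the error matters. The analysis is meant to support the comparability of the two materials. Putting some of one material into the other's column moves the two summaries closer together, so the error always favours the conclusion being examined.

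**Working it through.** **No figure to reproduce.** The documents give no sample size, margin, alpha or power for the process comparison; the SAP plans summary statistics only. The sample size calculation in Protocol Section 9.1 concerns the 4 stair climb and does not bear on this point.

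**The rules side by side.**

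| Comparison | Process 1 data defined by | Process 2 data defined by |
|---|---|---|
| C_trough, C2 (SAP 6.3.1.3.2) | Sequences 1 and 2, Period 1 | Sequence 3, Period 2, and at least 4 consecutive Process 2 doses |
| GDF-8 trough (SAP 6.3.2.2) | as for PK | as for PK |
| Immunogenicity (SAP 6.6.7) | Sequences 1 and 2 in Period 1; Sequence 2 in Period 2 | Sequence 3, Period 2, no prior Process 1 dose |

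Each Process 2 entry carries a condition on material received. No Process 1 entry does. Section 6.3.1.3.2 does drop known biased parameter estimates, but its example is an incomplete infusion, and it does not mention material.

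**Size of the dilution.** SAP Table 1 puts C_trough and C2 on the natural-log scale, and Section 6.3.1.3.2 lists geometric means, so the geometric mean ratio is the natural measure. Let

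- R = true Process 2/Process 1 geometric mean ratio (not in the documents; 0.80 assumed);
- f = share of the Process 1 column that is really Process 2 (not in the documents; 0% to 50% shown).

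The mean log value in the Process 1 column is then (1 − f) × log(Process 1) + f × log(Process 2). Subtracting it from log(Process 2) leaves (1 − f) × log R, so

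expected observed ratio = R^(1 − f).

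With R = 0.80:

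| f | Calculation | Expected observed ratio |
|---|---|---|
| 0% | 0.80^1.0 | 0.80 |
| 10% | 0.80^0.9 | 0.82 |
| 30% | 0.80^0.7 | 0.86 |
| 50% | 0.80^0.5 | 0.89 |

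Other assumed ratios behave in the same way. A true 0.70 appears as 0.725 at 10% and 0.837 at 50%; a true 1.25 appears as 1.222 at 10% and 1.118 at 50%.

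Arithmetic means, which the SAP also lists, give R / ((1 − f) + f × R). With R = 0.80 that is 0.80 / 0.94 = 0.851 at 30% and 0.80 / 0.90 = 0.889 at 50%, so the choice of mean hardly matters.

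**Simplifications.** One share is applied to all three dose levels. Under Section 2.3 a subject who has received Process 2 stays on it, so within a subject Week 45 is more likely to be affected than Week 13. The formula also treats each affected value as wholly Process 2; a value that follows a mixture of the two materials would dilute less.

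**The case against.** The best counter-argument is that the SAP sentence takes material as its subject. Read that way, it means that the Process 1 doses are to be found in Period 1, and a careful programmer would leave out Process 2 doses given there. The Process 2 filter already presumes that the process behind each dose is known. This reading is possible, but the table heading does not secure it, and there is no Process 1 condition to match the Process 2 one.

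The following objections stand, and they limit the point.

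- The fault is contingent. The general rule keeps Process 1 subjects on Process 1 through Period 1, and depletion is the exception. If no Sequence 1 or 2 subject received Process 2 in Period 1, the bias is zero. The documents do not say whether depletion occurred.
- The comparison is descriptive. No hypothesis, margin or decision rule is attached, and process comparability is not among the listed study objectives.
- At small shares the effect is small: a true 0.80 appears as about 0.82 at 10%.

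A reader might infer that immunogenicity has the same gap on both sides. It does not: Section 6.6.7 already bars prior Process 1 exposure for Process 2, and its source statements are permissive. A reader might also infer that the Process 1 column should simply mirror the four-consecutive-dose filter. That would remove subjects treated only with Process 1 who missed a dose, although Protocol Table 2 includes at least 3 doses at a level, not 4, among its conditions for escalation.

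**Conclusion.** The point holds as a one-sided gap. The Process 1 summaries for PK and GDF-8, and the Process 1 source for immunogenicity, are selected by sequence and period, while Section 2.3 provides for Process 2 in Period 1 after depletion. Followed as written, the table can place Process 2 data in the Process 1 column and shrink any true log difference by the factor (1 − f). With an assumed true ratio of 0.80, the expected observed ratio runs from 0.80 with no misclassification to 0.89 when half the column is Process 2. Both the ratio and the shares are assumptions.

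The documents do not support the stronger inference that a real difference has been, or will be, hidden. The effect is a partial dilution of a descriptive summary. It depends on whether supplies ran out during Period 1, and it may be nil. The primary efficacy analysis is not affected.

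**What to change.** In SAP Sections 6.3.1.3.2, 6.3.2.2 and 6.6.7, define the Process 1 summaries (PK, GDF-8, and anti-drug and neutralizing antibodies) by material actually received: include a subject at a visit only if all his active doses up to that visit were Process 1. List or summarise separately the Sequence 1 and 2 subjects who received any Process 2 in Period 1, and state how many there were.

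Keep the Process 2 rules unchanged: at least 4 consecutive Process 2 doses for PK and GDF-8, and no prior Process 1 for immunogenicity. A rule that looked only within each 16-week dose level would be weaker than the existing immunogenicity condition, because it would admit subjects with Process 1 at an earlier level. Do not add a four-consecutive-dose minimum to the Process 1 column.

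The cost is a few sentences in the SAP and some programming. No new data collection appears to be needed: the Process 2 filter already requires the process to be known dose by dose, the IRT assigns container numbers (Protocol Section 5.1), each carton carries a unique container number (Protocol Section 5.6.1), and the two processes use different vial sizes, 100 mg and 260 mg (SAP Section 2.3). The downside is that some subjects may leave the Process 1 column; the documents do not allow that number to be estimated.
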